Title: Radial Artery Vasodilation Heat Study

NCT: NCT03620383

Date: 8/27/2019

Study Protocol:

Study subjects

Institutional review board (IRB) approval will be obtained for this prospective, randomized, single-blinded controlled clinical trial (NCT03620383). Study subjects will be recruited from among healthy healthcare workers with no currently active vascular or chronic disease.

Exclusion criteria include prior history of left radial artery access. Study design and purpose were explained to the subjects prior to enrollment and written informed consent will be obtained.

Randomization

The census of the subjects will be enrolled in the study on a first-come-first-serve basis. The subjects will be randomized into palmar warming (“PaW”) and control groups based on a draw from a pool of paper slips with a group assignment written on them. The draw will be conducted without replacement from a pool of 60 slips equally divided into heat and no heat groups. To avoid violation of randomization, the study is designed to stop when one group reaches to its maximum predicted number.

Blinding

The sonographer will be unaware of the group assignment of the subjects. Also, to prevent sensing the temperature of the palmar pad, the sonographer will hold the probe from its proximal-most point and avoided contact or proximity with the subjects’ hand.

Intervention

The PaW group will be given a warm commercially available air-activated heat pack (Kobayashi Consumer Products LLC, Dalton, GA) to hold in the left hand for palmar warming. The control group will be given a de-activated version of the same heat pack to hold.

Radial artery cross-sectional area (CSA) measurement

Participants will be placed in a sitting position with their left forearm resting on a table. Before given the activated or de-activated heat pack, baseline left radial artery intraluminal height and width will be measured 2 cm proximal to the styloid process using an L20-5 linear array transducer with a ZS3 ultrasound system (Mindray Medical Systems, Inc, Mountain View, CA). A skin mark will be made at the site of measurement to ensure consistency in measurement location. The PaW group will then be given the activated heat pack and the control group will be given a de-activated heat pack. After 5 minutes of holding their respective heat packs, repeat left radial artery intraluminal height and width measurements will be obtained in both groups at the same location of the baseline measurement as indicated by the skin mark. Repeat height and width measurements will be again obtained after 10, 15, and 20-minutes of holding the assigned heat packs in both groups. Cross-sectional area (CSA) will be calculated according to the area for an ellipse based on height and width measurements. All sonographic measurements will performed by a single board-certified radiologist with two years of experience.

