Title: Radial Artery Vasodilation Heat Study

NCT: NCT03620383

Date: 8/27/2019

Statistical Analysis plan:

Statistical analysis will be performed using Stata v14.2 (StataCorp LLC, College Station, TX).

Categorical variables and numerical values will be reported as frequencies (percentage) and mean \pm standard deviation, and compared between two groups using the Chi² test and independent samples t-test, respectively. Trends in radial artery CSA will be compared between PaW and control groups using the repeated measure analysis of variance (rANOVA). P value < 0.05 was considered statistically significant in all analyses.

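### Does stopping enrolment when one arm is full undermine the 60-slip, 1:1 randomisation?

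*Protocol*

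**What the plan says.** The Randomization section of the Protocol describes a single pool with no blocks or strata. Subjects are allocated "based on a draw from a pool of paper slips with a group assignment written on them". On the make-up of the pool it says: "The draw will be conducted without replacement from a pool of 60 slips equally divided into heat and no heat groups". Half of 60 is 30 slips per arm, although the figure 30 is not printed. The next sentence ends enrolment early: "To avoid violation of randomization, the study is designed to stop when one group reaches to its maximum predicted number". The reason offered in its opening words is not explained further.

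The maximum is not stated as a number in either document, and there is no sample-size calculation, target power or target enrolment. The SAP compares groups by chi-squared test, independent-samples t-test and repeated-measures ANOVA at the 0.05 level. It mentions neither the stop rule nor unequal arms.

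**The concern.** An equally divided pool drawn without replacement has one main attraction: if every slip is used, the arms are exactly 30:30. The stop rule prevents this. When the 30th slip of one kind appears, the other arm has at most 29, so the study must end short of 60 and out of balance.

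The stated justification also looks weak. A full random ordering of 30 and 30 slips is valid randomisation, and using the last slips violates nothing. If so, the rule would give up subjects and balance, make the final sample size random, and gain nothing. If the unstated maximum were well below 30, the equal pool would no longer hold the arms together and the study could be much smaller than 60. At stake would be precision, and a reader's ability to check that enrolment ended when it should.

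**Working it through.** **Inputs.** Pool of 60, half per arm, so 60/2 = 30 each (Protocol, Randomization). Significance level 0.05 (SAP), taken as two-sided because sidedness is not stated. The maximum K is not given: K = 30 is assumed from the pool, with 25 and 20 shown as a range. The rule is assumed to count randomised subjects one at a time. The plan has no sample-size figure to reproduce.

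**Distribution at the stop.** The probability that one arm reaches K when the other has j (j < K) is

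P(j) = 2 × C(K+j−1, K−1) × C(60−K−j, 30−K) / C(60, 30).

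For K = 30:

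- Largest possible N is 30 + 29 = 59, so P(N = 60) = 0 and P(equal arms) = 0.
- P(30 v 29) is the chance that the last two slips in the full order differ: 30/59 = 0.508.
- P(difference ≥ 2) = 0.49; ≥ 3, 0.24; ≥ 5, 0.05.
- The 30 slips of one arm create 31 gaps, so on average 30/31 slips of the other arm lie after the last of them. Adding both directions, the expected unused tail is 2 × 30/31 = 60/31 = 1.94, and expected N = 60 − 1.94 = 58.06. A simulation of 100,000 shuffles gave 58.07.

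**What the unused tail is.** Those 1.94 slips are exactly the draws left after one arm has run out. All name the other arm, so each such assignment is known in advance. If all 60 slips were used, there would always be at least one.

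**Cost in power.** The documents give no effect size, so take the effect that yields 80% power at 30:30 (normal approximation): δ = (1.960 + 0.842) × √(2/30) = 0.723 SD. Power at n₁:n₂ is Φ(δ√(n₁n₂/(n₁+n₂)) − 1.960).

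- 30:29: √(870/59) = 3.840, giving Φ(0.818) = 79.3%.
- 30:28: √(840/58) = 3.806, giving Φ(0.793) = 78.6%.
- Averaged over the stopping distribution: 78.6%. Starting from 90%, the average is 89.0%.

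By the noncentral t distribution, the effect detectable with 80% power moves from 0.736 SD at 30:30 to 0.749 SD at 30:28.

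**Imbalance separated from size.** Efficiency relative to an equal split of the same N is 4n₁n₂/(n₁+n₂)². At 30:28 this is 3360/3364 = 99.9%. The average over the stopping distribution is 99.8%. Nearly all of the small loss comes from having about two fewer subjects, not from unequal arms.

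**Lower maxima (assumed).**

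| K | Expected N | P(difference ≥ 3) | P(difference ≥ 5) | Mean efficiency v equal split |
|---|---|---|---|---|
| 30 | 58.06 | 24% | 5% | 99.8% |
| 25 | 46.8 | 53% | 23% | 99.2% |
| 20 | 36.4 | 60% | 29% | 98.4% |

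Even at the lower values, imbalance costs under 2% of efficiency; most of the loss comes from the smaller N.

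**Bias.** The stop looks only at slip counts. Given that it occurs at 30 and j, every arrangement of the preceding 29 + j assignments is equally likely. No outcome enters the decision, so neither the estimate nor the type I error rate is distorted.

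**The case for a change.** The strongest case for acting has three parts.

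First, the maximum is never given as a number, so a reader cannot tell a study of about 58 from one of about 36, nor check that enrolment stopped on time. As a description of the documents this stands. But the pool points to 30, nothing in either document suggests a lower figure, and the gap is one of detail.

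Second, using every slip would be valid randomisation, so the stated reason is loosely worded. That also stands. It does not follow that the rule achieves nothing. At a maximum of 30 it removes every forced assignment, which is a natural reading of its purpose. It does not remove the growing predictability of earlier draws from a known pool, but neither would exhausting the pool. Someone must tally by arm to apply the rule, yet anyone who sees the allocations and knows the pool is half and half can keep the same tally without it.

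Third, pre-shuffled sealed envelopes used to the end would restore 30:30 at the cost of about two more volunteers. True, but this brings the forced assignments back, and envelopes do not hide them from anyone keeping count. It is a different trade-off, worth about one point of power.

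**Conclusion.** The literal observation is correct: under the stop rule the pool is never exhausted and the arms are never equal. With a maximum of 30, the consequence is an unbiased comparison of about 58 subjects, at 99.8% of equal-split efficiency, and about 1.4 points of power (80% to 78.6%). The rule gains the removal of 1.94 foreseeable assignments on average. No stated target enrolment or power is missed, because the documents set none; 60 is the number of slips. This is a fair trade-off, and the unstated maximum is a gap that the pool size fills sensibly. No change to the plan follows.

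The conclusion rests on three assumptions: the maximum is 30, the rule counts randomised subjects rather than completers, and tests are two-sided. If completers are counted, withdrawals could shift the final numbers. A maximum well below 30 would cost more, mainly through a smaller sample, but nothing in the documents points to one.

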Title: Radial Artery Vasodilation Heat Study

NCT: NCT03620383

Date: 8/27/2019

Statistical Analysis plan:

Statistical analysis will be performed using Stata v14.2 (StataCorp LLC, College Station, TX).

Categorical variables and numerical values will be reported as frequencies (percentage) and mean \pm standard deviation, and compared between two groups using the Chi² test and independent samples t-test, respectively. Trends in radial artery CSA will be compared between PaW and control groups using the repeated measure analysis of variance (rANOVA). P value < 0.05 was considered statistically significant in all analyses.

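### The planned CSA rANOVA uses baseline at best as a change score and designates no group difference; one named post-baseline contrast, adjusted for baseline CSA, would be more precise at almost no cost.

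*SAP*

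**What the plan says.** The protocol section on CSA measurement provides a reading before treatment in both arms: "Before given the activated or de-activated heat pack, baseline left radial artery intraluminal height and width will be measured". The first repeat comes at 5 minutes, and then: "Repeat height and width measurements will be again obtained after 10, 15, and 20-minutes of holding the assigned heat packs in both groups". All readings are taken at one skin mark by one operator, which gives five CSA values per subject.

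The SAP has one sentence specific to CSA: "Trends in radial artery CSA will be compared between PaW and control groups using the repeated measure analysis of variance (rANOVA". It does not state:

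- which term (group or group-by-time) is the treatment test;
- whether baseline is one of the levels;
- which time point or summary carries the main estimate;
- whether sphericity will be corrected for.

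No covariate is named. The sentence before it says that numerical values are summarised by mean and SD and compared by t-test, without saying whether this covers CSA at each time. The threshold is general: "P value < 0.05 was considered statistically significant in all analyses".

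On size, the Randomization section says: "The draw will be conducted without replacement from a pool of 60 slips equally divided into heat and no heat groups", and adds that "the study is designed to stop when one group reaches to its maximum predicted number".

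**The concern.** Two things are lost, and they should be kept apart.

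1. **No designated estimate.** A five-level group-by-time test has 4 numerator degrees of freedom. It can show that the curves differ, but it does not say by how much or when. If the t-test sentence is applied to CSA, it gives several unadjusted differences, none of them primary.
2. **Baseline is used inefficiently.** The group-by-time test works only on within-subject contrasts. Any contrast of post-baseline against baseline is then a change score, with the slope on baseline fixed at 1. ANCOVA estimates that slope from the data. When the correlation is below 1, the best slope is usually smaller and the residual variance lower.

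With fewer than 60 subjects, precision matters, and the covariate has already been collected. At stake are the width of the interval around the warming effect and whether the trial reports one prespecified effect at all.

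**Working it through.** The plan states no SD, correlation, effect size or power, so there is no figure of its own to reproduce. The calculations below use assumptions and show ranges.

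**Inputs**
- Five readings: baseline, 5, 10, 15 and 20 minutes (Protocol, CSA measurement).
- Pool of 30 + 30 slips, with enrolment ending when one arm is full (Protocol, Randomization). If the arm maximum is 30 (assumed), the largest sample is 30 + 29 = 59. The smaller arm is 29 with probability 0.51, averages 28.1, and is 25 or fewer with probability 0.05.
- Two-sided 5% level. The SAP gives 0.05; sidedness is assumed.
- Assumed: unit variance and compound symmetry with correlation r from 0.5 to 0.9.

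**Step 1: variance per subject, contrast held fixed**

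5-20 minute mean:
- change: (1+3r)/4 + 1 − 2r = 1.25(1−r)
- adjusted: (1+3r)/4 − r² = (1−r)(1+4r)/4
- ratio: (1+4r)/5

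20-minute value:
- change: 2(1−r)
- adjusted: 1 − r²
- ratio: (1+r)/2

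**Step 2: cost of estimating the slope**

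The expected variance inflation is 1 + 1/(N−4). At N = 59 this is 56/55 = 1.018, and at 30 vs 25 it is 52/51 = 1.020. Error degrees of freedom fall from 57 to 56.

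**Step 3: adjusted-to-change variance ratio, slope cost included (N = 59)**

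| r | 5-20 min mean | 20 min value |
|---|---|---|
| 0.5 | 0.61 | 0.76 |
| 0.7 | 0.77 | 0.87 |
| 0.8 | 0.86 | 0.92 |
| 0.9 | 0.94 | 0.97 |

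For example, at r = 0.8 the 5-20 minute mean gives (1+3.2)/5 × 56/55 = 0.84 × 1.018 = 0.86. Confidence intervals scale with the square root. For the 5-20 minute mean they are about 22% narrower at r = 0.5 (√0.61 = 0.78) and 3% narrower at r = 0.9 (√0.94 = 0.97).

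**Step 4: break-even**

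- 5-20 minute mean: (1+4r)/5 = 55/56 gives r = 0.978.
- 20-minute value: (1+r)/2 = 55/56 gives r = 0.964.

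Above these values adjustment loses to change, by at most 1/55 = 1.8% of variance.

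**Step 5: comparison with the omnibus test**

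This is a different question, because the contrast now changes too. Take r = 0.8, 30 vs 29, a peak effect of 0.5 SD (assumed) and 1/30 + 1/29 = 0.0678.

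- The omnibus test is noncentral F(4, 228) with λ = Σ(δ−δ̄)²/[(1−r) × 0.0678]. A flat effect gives 0.20/(0.2 × 0.0678) = 14.7; linear onset gives 0.156/(0.2 × 0.0678) = 11.5.
- The contrasts are noncentral t with noncentrality d/√(V × 0.0678), where V is the Step 1 variance. The adjusted V is multiplied by 56/55.

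| Effect at 5, 10, 15, 20 min (fraction of peak) | Omnibus | 5-20 mean: change → adjusted | 20 min: change → adjusted |
|---|---|---|---|
| Flat (1, 1, 1, 1) | 87.8% | 96.5 → 98.3% | 84.7 → 87.6% |
| Linear (0.25, 0.5, 0.75, 1) | 77.4% | 65.5 → 72.3% | 84.7 → 87.6% |
| Fading (1, 0.75, 0.5, 0.25) | 77.4% | 65.5 → 72.3% | 11.6 → 12.2% |

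Within each contrast, adjustment always helps here. Against the omnibus test, the result depends on whether the contrast fits the shape.

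**Step 6: sphericity**

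The null case was simulated with 30 vs 29, AR(1) correlation of 0.8, 0.9 and 0.95 between adjacent readings, and 10,000 runs each. The uncorrected group-by-time test rejected in 7.5%, 7.8% and 8.1% of runs. With the Greenhouse-Geisser correction it rejected in 4.7% to 4.9%.

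**The case against.** The best defence is that rANOVA is a standard analysis for serial readings, that the word trends asks a time-course question, and that baseline would normally be the first level. The mean, SD and t-test sentence may also supply arm means from which a reader could work out differences. Finally, one operator, one skin mark and five readings in 20 minutes make a high correlation plausible, and at 0.9 the covariate saves only 3% to 6% of variance.

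Most of this stands. The rANOVA is valid on its natural reading, and a planned single-degree-of-freedom contrast within it would supply an estimate without any covariate. What remains is that no such contrast or interval is planned, that the t-test differences would be unadjusted with none primary, and that the remaining efficiency gain is nearly free.

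A reader might infer three stronger things, none of which the documents support.

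- **That the plan ignores baseline or is biased.** Baseline is measured in both arms before the pack is given and probably enters as a level. Allocation is random.
- **That an adjusted contrast must beat the planned test.** Step 5 shows otherwise: with linear onset the adjusted 5-20 minute mean has 72% power against 77%, and with a fading effect the 20-minute value has 12% against 77%.
- **That a particular window, such as 15 and 20 minutes, should be primary.** Nothing in either document singles out a time. For a fading effect at correlation 0.8, that window would have 28% power against 77%.

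**Conclusion.** The point holds as a matter of efficiency and interpretability. The SAP designates no single CSA difference with an interval and does not use an available baseline as a covariate. For a fixed contrast, adjustment reduces variance relative to change by about 39% to 6% (5-20 minute mean) or 24% to 3% (20-minute value) as the correlation goes from 0.5 to 0.9. The cost is under 2% of variance, and break-even lies at a correlation of about 0.96 to 0.98. These sizes rest on assumed compound symmetry and an assumed correlation range. The power figures also assume the effect size, onset shape and arm sizes. No gain over the omnibus test is guaranteed. The one matter of validity is conditional: if correlation decays over time, an uncorrected group-by-time test rejects about 7-8% under the null.

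**What to change.** Before any group comparison, amend the SAP to:

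1. Name one post-baseline CSA summary that fits the time course the sponsor expects, for example the 5-20 minute mean or the 20-minute value, and give the reason for choosing it.
2. Estimate the group difference in that summary by ANCOVA with baseline CSA as covariate, and report it with a 95% CI as the main result.
3. Keep the rANOVA as the time-course test. State that group-by-time is the tested term and baseline the first level, and apply the Greenhouse-Geisser correction.
4. Say whether the t-tests cover CSA at individual times and, if so, label them descriptive or secondary.

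The cost is a few lines of SAP text and code and one error degree of freedom, with no new subjects or measurements. The real downside is lost power if the named summary misfits the onset shape. Retaining the omnibus test limits that risk but does not remove it.
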